In **AIM 2B**, we will assess endogenous striatal DA release in order to better understand altered striatal [C]raclopride binding, and (in **AIM 2C**) to replicate and extend pilot data that show that endogenous DA release in the dorsal caudate (DC) provokes inhibitory and anxiety symptoms in AN and BN. In brief, because [C]raclopride binding is influenced by endogenous DA, elevated [C]raclopride binding could indicate either an elevation of the density and/or affinity of the DA D2/D3 receptors or a reduction of intrasynaptic DA concentrations. It has been shown in non-human primate studies that the decrease in the BPND of benzamide radiotracers such as [C]raclopride following amphetamine (AMPH)-induced DA release is a reliable measure of endogenous DA transmission in striatal subdivisions (limbic, associative and sensorimotor striatum). AMPH administration results in an increase in extracellular DA and a consequent reduction in [C]raclopride binding. The change ( $\Delta$ ) in BPND (the difference between the [C]raclopride BPND at baseline and post-AMPH treatment normalized to the baseline BPND and expressed as a percentage) provides a non-invasive measure of changes in DA concentration in the human brain. We will use the PET/double [C]raclopride/AMPH paradigm described above to assess striatal endogenous DA release. Several recent, small scale studies using this technology and a previous study of cerebral spinal fluid (CSF) homovanillic acid (HVA), a DA metabolite, support the likelihood that REC AN and BN have alterations of endogenous striatal DA release. In AIM 2B we will assess endogenous DA release to help interpret alterations in DA functional activity as well as D2/D3 receptors in limbic, associative, and sensorimotor striatal regions. As summarized in **Table 1** we predict that endogenous DA release will be selectively diminished in limbic striatal regions in REC AN and in associative and sensorimotor regions in REC BN. These data argue that AN have diminished ability to direct “motivated” responses whereas BN may have hypoactive dorsal associative inhibitory pathways. Several lines of evidence support our hypothesis that alterations of food-induced DA secretion, perhaps acting on DA D2 receptors, contribute to pathologic eating. In **AIM 2C** we seek to replicate and extend findings that AN have a paradoxical response to palatable foods because endogenous DA release in the DC is anxiogenic in AN. This anxiogenic effect is compensated for by restricted eating to avoid anxiety. We will also test the hypothesis that a measure of altered inhibition in AN is associated with DC DA D2 binding.

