**Inhibition:** Clinically, it is well known that AN have exaggerated self-control and are anhedonic so they are able to sustain self-denial of food as well as most comforts and pleasures in life. For example, AN have an enhanced ability to delay reward (i.e., show less reduction in the value of a monetary reward over time) compared to healthy volunteers. This enhanced cognitive control and ability to delay reward may help to maintain persistent food restriction. We will build on a recent study in healthy controls that showed that striatal (particularly in dorsal regions) DA D2/D3 receptor availability was negatively correlated with speed of response inhibition [stop signal reaction time (SSRT)] and positively correlated with inhibition-related fMRI activation in frontostriatal neural circuitry. Thus people with faster stopping speed had more D2 receptor binding in the caudate and putamen. The stop signal task (SST) requires people to stop an already initiated response and calculates the speed of stopping (SSRT). There are relatively little response inhibition data (with SST or any other task) in AN, but a recent study in AN found that they had longer SSRT. Our data show that AN have normal DC D2 binding. However, as noted above, there is evidence that ill and recovered AN have reduced endogenous DA. Because AN may have less DA activating the DA D2 receptors, this may explain why their average inhibition ability is impaired. We will administer the SST after subjects complete the baseline [C]raclopride PET study. We predict (**Figure 1**) that both AN and CW will show a negative relationship between SSRT and DC D2 binding, but that such a relationship in AN will be shifted to the left due to reduced DA activation of the D2 receptor. While slower inhibition in AN may seem counter-intuitive, this finding may be consistent with studies that show they have impaired abilities to change mental set.

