We will repeat the SST after administration of AMPH. Studies tend to show that AMPH improves inhibition in healthy people without changing “going” speed. That is consistent with the idea that AMPH induced release of endogenous DA increases activation of D2 receptors and thus underlies inhibition-related caudate activity. We expect to find that AMPH shifts healthy controls to the right (**Figure 1**). An abnormal shift to the right in AN would suggest aberrant function of DA/D2-related processes. It is possible that higher anxiety in AN contributes to the slower stopping speed. While low threat puts people in a state of arousal where they can stop things more quickly, high threat association appears to make them slower. We will stratify our AN population into high and low state anxiety groups to better understand the relationship between anxiety and response inhibition ability in this group, and how that relates to the AMPH challenge and a putative marker of endogenous DA. Overall, too few data exist to be certain that the SST is an adequate reflection of inhibitory control ability in AN (especially in a way that relates to self-control). Individuals with BN and AN-BN have a puzzling group of symptoms in that they alternate between being overly inhibited and overly disinhibited: eating behaviors tend to alternate between restriction and overeating with a loss of normal meal patterns. This study will provide the opportunity to better understand relationships between [C]raclopride

BPND or DA release and measures of inhibition and anxiety in BN and AN-BN.

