**Aim 2C** Relationships between [C]raclopride  $\Delta$  BPND and behavioral characteristics (from assessments and VAS scales) and plasma AMPH levels of subjects will be analyzed with Pearson Product-Moment correlation coefficient. For example, we will compare the Fisher's z-transformed correlations between behavioral measures of euphoria and anxiety with [C]raclopride  $\Delta$  BPND in REC AN, REC AN-BN and REC BN vs. CW using a t-test. Based on our pilot data in REC AN, we expect correlations between euphoria and [C]raclopride  $\Delta$  BPND in the AVS to be larger (in magnitude) than -0.69 in CW and 0.21 in REC AN subjects. Assuming a difference in Fisher's z-transformed correlations of 1.06 (or larger), we will have power 0.91 to see a group difference at the 0.05 level (two-sided), with 20 subjects per group. (Note that the z-transformed value of 0.69 is -0.85, and the z-transformed value of 0.21 is 0.21, giving a difference of 0.21 - (-0.85) = 1.06). Similarly, we will correlate DA release with self-ratings of anxiety, euphoria, self-control, and labile mood in striatal regions in order to assess behavioral response, as well as SSRT and post-study food consumption. We will use continuous

measures of impulse control and inhibition including the SSS, BIS-11, EDI-2-subscale impulse regulation, novelty seeking and HA from the TCI and the basic stop signal task. It is not certain what to expect from the REC BN and REC AN-BN subjects, but we will look for differences in correlations in the same way. Assuming these differences are larger than 0.909, we will have power in excess of 0.80 to see group differences at the 0.05 level (two-sided). We will explore the effects of age, height, and weight on DA release using partial correlations, after controlling for these variables.

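### Aim 2C names no analysis of SSRT against baseline dorsal caudate binding, and comparing correlations cannot show the shift predicted in AN; the HA hypothesis also lacks a test, and two stated powers are slightly too high at 20 per group

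*Combined protocol and SAP*

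**What the plan says.** **The hypothesis.** Section 6 (Specific Aims), Aim 2C: "We will also test the hypothesis that a measure of altered inhibition in AN is associated with DC DA D2 binding".

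**The prediction.** Section 7, under Inhibition, expects a negative relation between SSRT and DC D2 binding in both AN and control women (CW), "but that such a relationship in AN will be shifted to the left due to reduced DA activation of the D2 receptor". For amphetamine (AMPH) it adds: "We expect to find that AMPH shifts healthy controls to the right". The Figure 1 caption describes SSRT against baseline raclopride BP_ND, with an arrow for the post-AMPH change.

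**The analysis.** The Aim 2C paragraph of the Power and Statistical Analysis Plan correlates dopamine (DA) release, that is ΔBP_ND, with self-ratings "in order to assess behavioral response, as well as SSRT and post-study food consumption". The stop signal task appears once more, in a list of continuous "measures of impulse control and inhibition including the SSS" and other scales, with no binding variable or model attached. Groups are compared by a t-test on Fisher z-transformed correlations. For REC BN and REC AN-BN the outcome is uncertain, "but we will look for differences in correlations in the same way". Partial correlations are named only to control for age, height and weight.

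**The stated power.** 0.91 for a Fisher z difference of 1.06 with 20 per group, and more than 0.80 for a difference of 0.909 (n not restated), both two-sided at 0.05. Section 10 plans 25 completers per group.

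**Harm avoidance (HA).** Section 6 gives, as the second Aim 2A hypothesis, an association of DC BP_ND with HA in recovered eating-disorder (REC ED) women. The Aim 2A analysis paragraph names t-tests by diagnosis and a regression of log BP_ND on group, age, height and weight. It also mentions other relevant variables, without naming HA.

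**The concern.** Two things do not line up. First, the hypothesis concerns baseline binding, while the only binding variable paired by name with SSRT is DA release. These are different quantities: one is the level of BP_ND before AMPH, the other its relative change after AMPH.

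Second, a negative slope is predicted in both groups, so the AN-specific part of the prediction is the shift. The only between-group method in the Aim 2C text compares correlations, and a correlation does not depend on where a line sits.

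If the text is followed as written, the association stated in the Specific Aims and the shift predicted in the Background have no prespecified test, although the SSRT and BP_ND data for both are collected. The HA hypothesis of Aim 2A is in the same position. The power statements raise a separate question: a t-test needs replicate observations, but each group supplies a single correlation.

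**Working it through.** **1. Why a shift is invisible to correlations.** Let SSRT = a + b·BP_ND + error in CW. Moving the AN line sideways by h gives a + b·(BP_ND + h) = (a + b·h) + b·BP_ND. The slope is unchanged and the intercept moves by c = b·h. Since corr(x, y + c) = corr(x, y), both within-group correlations stay the same, at any sample size. A group term estimates c directly.

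**2. Simulation of that identity.** Assumptions, since the documents give no SSRT mean, SD or slope: within-group r of -0.3, -0.5 and -0.7; equal mean DC BP_ND (the Background says AN have normal DC binding); parallel shift in residual SDs; 100,000 runs per cell.

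| Shift (residual SD) | Comparing correlations, n=25 | Group term, n=25 | Group term, n=20 |
|---|---|---|---|
| 0.5 | 0.048-0.050 | 0.40 | 0.33 |
| 0.8 | 0.048-0.050 | 0.78 | 0.68 |
| 1.0 | 0.048-0.050 | 0.93 | 0.86 |

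The second column is the type I error rate. The last two describe the proposed test under assumed shifts; they do not measure a loss in the plan.

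**3. Reproducing the stated power.** z(-0.69) = -0.848 and z(0.21) = 0.213, difference 1.061, as in the plan. If each z is given variance 1/n, as in a unit-SD two-sample t-test with n = 20, then SE = √(2/20) = 0.316 with 38 df:
- 1.06/0.316 = 3.35, power 0.904 (stated 0.91).
- 0.909/0.316 = 2.87, power 0.800 (stated >0.80). The 80%-detectable difference of this test is 0.9091.

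The normal version gives 0.918 and 0.820. The stated figures are therefore consistent with a variance of 1/n; that this is how they arose is an inference.

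**4. The Fisher z calculation.** The variance is 1/(n-3), so SE = √(1/(n₁-3) + 1/(n₂-3)) and power ≈ Φ(d/SE - 1.96).
- n = 20: SE = √(2/17) = 0.343. For 1.06, Φ(3.09 - 1.96) = 0.871. For 0.909, Φ(2.65 - 1.96) = 0.755.
- n = 25: SE = √(2/22) = 0.302. For 1.06, 0.940. For 0.909, 0.854.

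Simulation with 200,000 runs gives slightly more: 0.887 and 0.775-0.778 at n = 20; 0.949 and 0.867-0.869 at n = 25. By the formula, 23 per group are needed for 0.91 at 1.06, and 22 for 0.80 at 0.909.

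**5. HA.** With 3 × 25 = 75 REC ED women, the correlation detectable with 80% power is tanh((1.96 + 0.84)/√72) = 0.32. A plain test is feasible; it is just not stated.

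**The case against.** The strongest reply is that this is an omission rather than a wrong test. The Specific Aims state an association, which a Pearson correlation would address. The shift appears only in the Background, which itself warns that too few data exist to be sure the task reflects inhibitory control in AN. That is fair. A reader might infer that the plan offers the comparison of correlations as its test of the shift; it never does. What stands is narrower: even the plain association with baseline DC BP_ND is not named, and no other listed method reaches the shift.

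A second reply is that the Stop Signal Task section scores SSRT by a method chosen with group differences in mind, and that with equal mean BP_ND a shift is simply a difference in mean SSRT, which a plain group comparison would detect. This is also true, but the section names no such comparison.

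A reader might go further and see a contradiction in direction. On conventional axes, moving a falling line left means lower SSRT at a given binding, whereas the text says "While slower inhibition in AN may seem counter-intuitive"; moving it right means higher SSRT, whereas the text says "that AMPH improves inhibition in healthy people without changing" the speed of going. The documents do not support calling this an error. Figure 1 is not shown here, and a reversed axis, or group means moving along a shared band, would remove the tension. Nor would the direction be left until the data are seen: those same sentences state it in SSRT terms.

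Finally, the power error has little practical effect, and the 0.909 sentence gives no n. Both points stand.

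**Conclusion.** The concern holds as a gap between hypothesis and analysis. The SSRT hypothesis about baseline DC binding has no named analysis, and the group comparison that is named cannot show the predicted shift. That conclusion follows from step 1 and needs no assumed effect. How large a shift the added test would detect does depend on assumptions and is not a finding against the plan. The HA hypothesis of Aim 2A likewise has no named test.

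The powers for comparing correlations are wrong as written, by a small amount. At 20 per group, 0.91 should be 0.87-0.89. The figure of more than 0.80 should be 0.76-0.78 if that sentence carries over n = 20. At 25 completers per group both stated powers are met.

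The point is worth correcting before analysis. It does not threaten the study.

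**What to change.** 1. Under Aim 2C, prespecify SSRT = a + b·(baseline DC BP_ND) + c·group, with a check of group × BP_ND. Test b for the association and c, two-sided, for the shift. The Aim 2B model already has this form, with a baseline covariate and a group term.
2. For the AMPH prediction, add a paired or mixed model of baseline and post-AMPH SSRT with session, group and group × session.
3. Under Aim 2A, state the correlation or regression of HA on baseline DC BP_ND in REC ED women.
4. Replace the t-test on correlations by the Fisher z-test with SE = √(1/(n₁-3) + 1/(n₂-3)). Restate power at 20 per group as 0.87-0.89 (difference 1.06) and 0.76-0.78 (difference 0.909), or quote 0.94-0.95 and 0.85-0.87 at 25 per group. Give the n in both sentences.

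The cost is SAP wording and a few extra models. No new data are needed.

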On the following day, the second day of the study, they will be awakened at 7:00 A.M. by the research staff. After a light breakfast, they will be transported again by taxi to the UCSD NeuroPET Center. After insertion of another intravenous catheter and following another transmission scan, the first PET scan will be acquired following a slow IV bolus administration (over 20 sec) of 10 mCi of high-specific activity [C]raclopride. Emission data will be collected in 3D mode for 60 minutes using a standard PET protocol as previously described. The participant will then be able to rest outside the scanner and will receive a physical exam, mental status exam, EKG, and vital signs measurement. The IV will stay in place. Thirty minutes following the first scan with [C]raclopride, the participant will receive 0.5 mg x kg of oral AMPH. Blood pressure and heart rate will be recorded every two minutes for the first 15 minutes, every five minutes for the next 30 minutes, and then every 15 minutes (up to at least 180 min). The post-AMPH [C]raclopride scan will be performed 3 hours after the administration of AMPH. Assessment of behavioral responses will be conducted before and after PET scans. The participants will complete a symptom-rating visual analog scale (VAS) pre-baseline PET, pre-AMPH, and then at 30 minute intervals a questionnaire assessing several states: "happy," "anxious," "energetic," "restless." To assess study participants' mood states and fluctuations, we will utilize, at the same intervals, the short version of Profile of Mood States (POMS-B). The POMS is a useful measure of mood states and their fluctuations and is appropriate for both research and therapy. It is a factor-analytically derived self-report inventory that measures six identifiable mood or affective states: tension-anxiety; depression-dejection; anger-hostility; vigor-activity; fatigue-inertia; and confusion-bewilderment. For more than 30 years, the POMS assessment has provided a valid and reliable measure of affective mood states. The short version, POMS Brief, developed in 1989, has a total of 30-items with five on each of the six POMS factors. Like the longer version, the POMS-B has excellent internal consistency. Items are rated on a 5-point scale (not at all, a little, moderately, quite a bit, extremely) and they only take five minutes to complete. The items are easy for patients to understand, allowing them to quickly and accurately complete the assessment. The basic stop signal task will be done after the 1st [C]raclopride (at baseline) and then shortly after the 2nd [C]raclopride (post-AMPH) scan. The study will be completed by approximately late afternoon. At the completion of the second scan, the IV lines will be removed. An EKG, vital signs, mental status and physical exam will be performed and evaluated by the study physician prior to the subject's discharge from the PET suite. The subject will be served a cafeteria-style assortment of lunch foods following the [C]DASB scan on Day 1 and the post-AMPH [C]raclopride scan on Day 2. The uneaten food will be weighed after completion of the meal and the total calories consumed will be recorded.

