[C]DASB will be prepared at the UCSD Center For Molecular Imaging, PET Radiochemistry Laboratory. Radioactive [C]CO2 will be produced by the N(p, α)C nuclear reaction at the CTI RDS 111 cyclotron operated by PETNET. The [C]CO2 will be converted into [C]CH3I desmethyl-DASB precursor that is reacted using the loop injection port procedure. Then, the contents of the HPLC loop will be quantitatively injected into a semi preparative liquid chromatography column. The product will be transferred into a flask containing a multiple volume (10x with respect to the product peak volume) of HPLC water. After that the aqueous solution is pushed through a solid phase extraction cartridge containing C-18 (usually WATERS SepPak light C-18 cartridge). The product is retarded on the C-18 cartridge. The cartridge is washed with 10 ml sterile water followed by product extraction with 1 ml USP EtOH transferred into a sterile product vial already containing 19 ml isotonic saline using a 22 μm sterile Millex-FG membrane filter. Quality Assurance will be performed as recommended by the FDA. The total synthesis time will be 50± 5 min. The average specific activity at the end of the analysis has averaged 1000 to 5000 Ci/mmol. The studies are carried out under IND 74, 254 for [C]DASB.

Dextroamphetamine sulfate (oral) is the dextro isomer of the compound d,l-AMPH sulphate. It is an FDA approved drug available for the treatment of narcolepsy and attention deficit hyperactivity disorder (maximum approved total daily dose of 5-60 mg). It is manufactured and marketed under the commercial name Dexedrine by GlaxoSmithKline pharmaceuticals. As dexedrine is available as an orange, triangular, scored tablet in 5 mg, 10 mg and 15 mg strengths, it will be dispensed by the pharmacy as nearly as it can be approximated to 0.5 mg/kg (in 2.5 mg increments). For example a subject who weighs 50 kg or 54 kg will receive 25 mg of AMPH, while a subject who weighs 55 kg will receive 27.5 mg of AMPH. The use of AMPH in this study will be in an off-label manner. The pharmacokinetics and behavioral effects of oral dextroamphetamine peaks at 3h. Several other groups have successfully used oral AMPH in the dose range of 0.43-0.5 mg/kg in PET imaging studies.

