
**Transfer Criteria:** The subject will be transferred from the UCSD PET center to the UCSD Eating Disorder Treatment and Research Center once they meet the following criteria upon evaluation by a study physician: a blood pressure of less than 150/90 mm Hg; a heart rate of less than 110 BPM; no behavioral abnormalities.

**Discharge Criteria:** After a minimum of 6 hours of observation following drug ingestion, the subject will be medically discharged from the UCSD Eating Disorder Treatment and Research Center only if they meet the following criteria upon evaluation by a study physician: a) a blood pressure (BP) of less than 20 mm Hg above

their baseline reading for systolic and diastolic BP or less than 150/90 (whichever reading is lower); b) a heart rate of less than 20 BPM above their baseline or 100 (whichever reading is lower); c) no reported subjective effects from the AMPH; d) no adverse events to the AMPH; e) a normal physical exam; f) a normal mental status exam. Most of the REC AN and BN will travel to San Diego for this study. We will establish a policy that they are required to stay the night after the study and will be discharged to travel home the next day. For the subjects that live in San Diego, we will ask a relative to drive them home after being discharged from the study.

**Confidentiality.** To minimize possible risk of breach of confidentiality, each study participant will be assigned, upon entry into the study, a numeric code which will be used as the identifier for subsequent research related activities. All information collected, including self-report questionnaires, psychological assessments, and imaging data are identified solely by these numbers without any personal identifiers. Only strictly anonymous data will be entered into the database and used for statistical analysis. Access to the numbering system will be limited to the principal investigators, Drs. [name] and [name], and their research staff involved in the study. Research files will be kept in locked quarters and made available only to qualified personnel for research purposes. No verbal or written information concerning a subject will be released to anyone without expressed written consent by the subject.

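### Aim 2C relates dopamine release to food intake without naming the meal, and gives the drug-free Day-1 lunch no role as a reference for the lunch eaten after amphetamine

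*Combined protocol and SAP*

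**What the plan says.** Section 9 of the combined protocol and SAP (Power and Statistical Analysis Plan, Aim 2C) correlates dopamine release, measured as the change in raclopride BPND, with self-ratings "as well as SSRT and post-study food consumption". The food variable is not defined further. Partial correlations are planned for age, height and weight. Plasma amphetamine is to be correlated with the change in BPND but is not named as an adjustment for intake.

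Study-Day Session Procedures, also in section 9, provides two lunches: "The subject will be served a cafeteria-style assortment of lunch foods following the" DASB scan on Day 1, when no amphetamine is given, and again after the post-amphetamine raclopride scan on Day 2. It continues: "The uneaten food will be weighed after completion of the meal and the total calories consumed will be recorded".

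On Day 2 the second raclopride "scan will be performed 3 hours after the administration of AMPH". Of the drug, the dextroamphetamine paragraph says: "The pharmacokinetics and behavioral effects of oral dextroamphetamine peaks at 3h". Section 15 allows medical discharge only "After a minimum of 6 hours of observation following drug ingestion".

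Section 6 gives the reasoning behind Aim 2C. Dopamine release in the dorsal caudate is said to provoke anxiety in AN, and then: "This anxiogenic effect is compensated for by restricted eating to avoid anxiety".

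**The concern.** The food correlation will be read against that reasoning. Day-2 calories have at least two components: how much the woman usually eats at such a lunch, and how she responds to the challenge. A correlation with Day-2 calories alone cannot separate them. If release is linked to habitual intake only, a correlation still appears on Day 2 and can be taken for a response to dopamine release. If release is linked to the response only, habitual differences between women add noise and shrink the correlation.

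The plan gives its other challenge outcomes a drug-free reference. Aim 2B models post-amphetamine BPND on baseline BPND. The stop signal task is run at baseline and again after amphetamine. Mood ratings are collected for contrast with baseline. Blink rate is recorded before each raclopride scan. Food intake is also measured with and without drug, but no contrast is specified. With the meal unnamed, the choice between Day 1, Day 2 and a change could be made after the results are seen.

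**Working it through.** **1. Timing of the Day-2 lunch.** The second raclopride scan starts 3 h after the dose. For the first raclopride scan the plan says: "Emission data will be collected in 3D mode for 60 minutes". Assuming the second lasts as long, lunch comes no earlier than 3 h + 1 h = 4 h after the dose. That is about 1 h past the stated 3 h peak.

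**2. The plan's own power figures.** No power is stated for food intake. The Aim 2C example (euphoria) uses a Fisher-z difference of 0.213 + 0.848 = 1.06 with 20 per group, two-sided 0.05, and states power 0.91. A two-sample t-test with unit SD (noncentrality 1.06 × √(20/2) = 3.35, 38 df) gives 0.904. The second statement (difference 0.909, power above 0.80) gives 0.800. Both reproduce that way. The usual standard error √(2/(n − 3)) gives 0.871 and 0.755.

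**3. Cost of one covariate.** Adding Day-1 calories replaces n − 3 by n − 4 in each group, with power = Φ(d/√(2/(n − 3 − k)) − 1.96) and k covariates.

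| d | n per group | k = 0 | k = 1 |
|---|---|---|---|
| 1.06 | 20 | 0.871 | 0.850 |
| 1.06 | 25 | 0.940 | 0.930 |
| 0.909 | 20 | 0.755 | 0.729 |
| 0.909 | 25 | 0.854 | 0.838 |

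The cost is 1 to 2 points on the plan's example and at most about 2.6 points in the table.

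**4. Gain if release relates only to the response.** In standardised form, let Day-2 = ρ × Day-1 + residual, with release correlated 0.5 with the residual and unrelated to Day-1 intake. The unadjusted correlation is 0.5 × √(1 − ρ²). Within-group power is Φ(atanh(r) × √(n − 3 − k) − 1.96), here at n = 25. The documents give no ρ, so a range is assumed.

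| ρ (assumed) | Unadjusted r | Power unadjusted (k = 0) | Power adjusted (k = 1) |
|---|---|---|---|
| 0.3 | 0.48 | 0.68 | 0.71 |
| 0.5 | 0.43 | 0.59 | 0.71 |
| 0.7 | 0.36 | 0.42 | 0.71 |
| 0.8 | 0.30 | 0.31 | 0.71 |

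The adjusted figure depends on the degrees of freedom charged: 0.73 with none, 0.71 with one, 0.69 with two (if plasma amphetamine were added). The planned age, height and weight terms are left out of both columns.

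**5. Error if release relates only to habitual intake.** Let release correlate 0.5 with Day-1 intake and not at all with the residual. The unadjusted Day-2 correlation is 0.5 × ρ: 0.15 at ρ = 0.3, 0.25 at 0.5 and 0.40 at 0.8. With Day-1 intake partialled out it is 0.

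**The case against.** The best reply is that this is an undefined variable in a secondary analysis. Food intake comes late in a list of correlates, with no stated direction, hypothesis or power. Section 7 gives the major goal of Aim 2C as harm avoidance with baseline binding, and anxiety with release. That is right and limits the weight of the point. It does not remove it, because both lunches are collected and the plan does not say how to use them.

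A second reply is that measuring behaviour on drug is the purpose of a challenge study. This also stands: the on-drug meal is not the defect. The defect is the missing reference.

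A third is that adjustment changes the question. In a study of persistent traits, partialling out Day-1 intake removes any link with habitual eating (step 5). This is why the Day-1 correlation should be reported alongside the adjusted one.

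Four stronger readings are tempting but not supported.

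- A reader might infer that the plan rejects the Day-1 meal. It is only silent, and its term could cover either lunch.
- A reader might blame the longer wait before the Day-2 lunch. The schedule is common to all women, so it shifts mean intake and cannot by itself bias a correlation between women.
- A reader might infer that anxiety is never rated around a meal. Section 9 schedules Day-2 ratings at 30-minute intervals with no stated end, and behavioural assessments before and after the scans.
- A reader might assume a known effect of amphetamine on appetite. Sections 14 and 15 list nausea, vomiting and abdominal cramping, which could affect eating, but the documents do not quantify any effect on intake.

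**Conclusion.** The point holds as a gap in the Aim 2C analysis. The meal is unnamed, and a drug-free baseline already collected in the same woman has no role. As written, a correlation with Day-2 calories could reflect habitual intake, the response to the challenge, or both.

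The size rests on assumptions about the meal-to-meal correlation. At 0.3 the power gain from adjustment is about 3 points (0.68 to 0.71), and below that it may be nil. At 0.7 it is about 29 points (0.42 to 0.71). These figures assume a partial correlation of 0.5, n = 25 and no link between release and Day-1 intake. In the opposite case a correlation of 0.15 to 0.40 would appear with no relation to the challenge response. The value of 0 after adjustment assumes that release relates to Day-1 calories as measured. One lunch is an imperfect gauge of habitual intake, so some of the link could remain. The change is worth making before analysis, but it does not affect the main comparisons of the study.

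**What to change.** In the Aim 2C analysis text:

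- Name the meal. Define the challenge food outcome as Day-2 calories adjusted for the same woman's Day-1 calories, by partial correlation or by a regression that includes the change in BPND and Day-1 calories.
- Report the correlation of the change in BPND with Day-1 calories separately, as the habitual-intake measure.
- Show adjustment for plasma amphetamine only as a sensitivity analysis, with and without the term. Exposure also drives release, so adjusting for it may remove part of the relation of interest.
- State how a missing Day-1 meal is handled. The progress report counts 46 DASB and 47 raclopride scans, the difference being one control woman, so at least one Day-1 lunch may be absent.

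The cost is wording and one degree of freedom. No new measurement is needed, and women already scanned can be included where both lunches were recorded as section 9 requires.
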